6.2 Exclusion Criteria

1) Target Disease Exceptions

- a) Participants with known or suspected CNS metastases, untreated CNS metastases, or with the CNS as the only site of disease are excluded. However, participants with controlled brain metastases will be allowed to enroll. Controlled brain metastases are defined as no radiographic progression for at least 4 weeks following radiation and/or surgical treatment (or 4 weeks of observation if no intervention is clinically indicated), and off of steroids for at least 2 weeks, and no new or progressive neurological signs and symptoms. Please note: SCCHN participants with direct extension of tumor through the base of skull will not be excluded, as they are considered distinct from hematogenously spread parenchymal brain metastasis.
- b) Participants must not have ocular melanoma.

2) Medical History and Concurrent Disease

- a) Participants must not have a personal or family history or presence of cytochrome b5 reductase deficiency, or other diseases that puts them at risk of methemoglobinemia.
- b) Participants must not have a prior history of serotonin syndrome.
- c) Participants must not have a history of or current G6PD deficiency (quantitative or qualitative assessments will be checked during screening). Participants must also not have any other congenital or autoimmune hemolytic disorders. If participant has history of transient acquired hemolytic anemia, discuss with medical monitor for study eligibility.
- d) Participants must not have a history or presence of hypersensitivity or idiosyncratic reaction to methylene blue.
- e) Participants with a prior malignancy are excluded (except non-melanoma skin cancers, and *in situ* cancers such as the following: bladder, colorectal, cervical/dysplasia, melanoma, or breast). Participants with other second malignancies diagnosed more than 2 years ago who have received therapy with curative intent with no evidence of disease during the interval who are considered by the investigator to present a low risk for recurrence will be eligible.
- f) Participants must not have other active malignancy requiring concurrent intervention.
- g) Participants must not have prior organ allograft or allogeneic bone marrow transplantation.
- h) Participants must not have any anti-cancer therapy (eg, chemotherapy, biologics, vaccines, or hormonal treatment) including investigational drugs within 4 weeks prior to the first dose of study drug administration, except for non-cytotoxic therapies, for which at least

4 weeks or 5 half-lives (whichever is shorter) must have elapsed between last dose and first treatment with any study drugs; if 5 half-lives is shorter than 4 weeks, agreement with the Medical Monitor must be obtained.

- i) Participants must not have had prior therapy with an IDO inhibitor.
- j) Participants must not have active, known, or suspected autoimmune disease. Participants with vitiligo, type 1 diabetes mellitus, residual hypothyroidism due to autoimmune condition only requiring hormone replacement, euthyroid participants with a history of Grave's disease (participants with suspected autoimmune thyroid disorders must be negative for thyroglobulin and thyroid peroxidase antibodies and thyroid stimulating immunoglobulin prior to first dose of study drug), psoriasis not requiring systemic treatment, or conditions not expected to recur in the absence of an external trigger are permitted to enroll.
- k) Participants must not have a condition requiring systemic treatment with either corticosteroids (> 10 mg daily prednisone equivalents) or other immunosuppressive medications within 14 days of study drug administration.
Note: Treatment with a short course of steroids (< 5 days) up to 7 days prior to initiating study drug is permitted.
- l) Participants must not require daily supplemental oxygen.
- m) Participants must not have uncontrolled or significant cardiovascular disease including, but not limited to, any of the following:
 - i) Myocardial infarction or stroke/transient ischemic attack within the past 6 months.
 - ii) Uncontrolled angina within the past 3 months.
 - iii) Any history of clinically significant arrhythmias (such as ventricular tachycardia, ventricular fibrillation, or Torsades de pointes).
 - iv) QT interval corrected for heart rate using Fridericia's formula (QTcF) prolongation ≥ 480 msec.
 - v) History of other clinically significant heart disease (eg, cardiomyopathy, congestive heart failure with New York Heart Association functional classification III-IV, pericarditis, significant pericardial effusion, or myocarditis).
 - vi) Cardiovascular disease-related requirement for daily supplemental oxygen therapy.
- n) Participants must not have a history of any chronic hepatitis as evidenced by:
 - i) Positive test for hepatitis B surface antigen.
 - ii) Positive test for qualitative hepatitis C viral load (by polymerase chain reaction [PCR]).
Note: Participants with positive hepatitis C antibody and negative quantitative hepatitis C by PCR are eligible. History of resolved hepatitis A virus infection is not an exclusion criterion.
- o) Participants must not have a history of other preexisting liver disease (eg, nonalcoholic fatty liver disease [NAFLD]).
- p) Participants must not have significant gastrointestinal disease, or other conditions known to interfere significantly with the absorption of oral medication. Contact BMS medical monitor/designee if needed.

- q) Participants must not have active interstitial lung disease/pneumonitis or with a history of interstitial lung disease/pneumonitis requiring steroids.
- r) Participants must not show evidence of active infection \leq 7 days prior to initiation of study drug therapy (does not apply to viral infections that are presumed to be associated with the underlying tumor type required for study entry).
- s) Participants must not have a known history of testing positive for human immunodeficiency virus (HIV) or known acquired immunodeficiency syndrome (AIDS).
Note: Testing for HIV must be performed at site.
- t) Participants must not show evidence or history of active or latent tuberculosis infection including PPD recently converted to positive; chest x-ray with evidence of infectious infiltrate; and recent unexplained changes in fever/chill patterns.
- u) Participants must not have had any major surgery within 4 weeks of study-drug administration. Participants must have recovered from the effects of major surgery or significant traumatic injury at least 14 days before the first dose of study drug.
- v) All toxicities attributed to prior anti-cancer therapy other than alopecia and fatigue must have resolved to Grade 1 (National Cancer Institute Common Terminology Criteria for Adverse Events [NCI CTCAE] v5.0) or baseline before administration of study drug. Participants with toxicities attributed to prior anti-cancer therapy that are not expected to resolve and result in long lasting sequelae, such as neuropathy after platinum based therapy, are permitted to enroll.
- w) Participants must not have a history of life-threatening toxicity related to prior immune therapy (eg, anti-CTLA-4 or anti-PD-1/PDL-1 treatment or any other antibody or drug specifically targeting T-cell co-stimulation or immune checkpoint pathways).
- x) Participants must not have a known or underlying medical condition that, in the opinion of the investigator or sponsor, could make the administration of study drug hazardous to the participants, or could adversely affect the ability of the participant to comply with or tolerate the study.

3) Prior/Concomitant Therapy

- a) Participants must be able to comply with restrictions and prohibited treatments as listed in [Section 7.7](#), Concomitant Therapy.
- b) Participants with prior exposure to anti PD-1 or anti-PDL1 therapy must be excluded.
- c) Participants must not use any strong inhibitors of CYP3A4 and/or CYP1A2 or strong inducers of CYP3A4 and/or CYP1A2 (see [Appendix 8](#)).
- d) Participants must not use non-oncology vaccines containing live virus for prevention of infectious diseases within 12 weeks prior to study drug. The use of inactivated seasonal influenza vaccines will be permitted on study without restriction.
- e) Participants must not use packed red blood cells or have a platelet transfusion within 2 weeks prior to the first dose of study drug.
- f) Prior Traditional Chinese Medicines (TCMs) are not prohibited; however, prior TCMs with anti-cancer claims should be stopped for at least 14 days prior to dosing. Prior use of TCMs is not considered prior-line of therapy.

4) Physical and Laboratory Test Findings

- a) Participants must not exhibit any of the following on a 12-lead ECG prior to study drug administration, confirmed by repeat:
 - i) QRS \geq 120 msec, except right bundle branch block
 - ii) QTcF \geq 480 msec, except right bundle branch block

5) Allergies and Adverse Drug Reaction

- a) Participants must not have a history of allergy to any of the study treatment components.
- b) Participants must not have a history of any significant drug allergy (such as anaphylaxis or hepatotoxicity) to prior anticancer immune-modulating therapies (for example, checkpoint inhibitors and T cell costimulatory antibodies).

6) Other Exclusion Criteria

- a) Prisoners or participants who are involuntarily incarcerated are excluded from the study. (Note: Under certain specific circumstances a person who has been imprisoned may be included or permitted to continue as a participant. Strict conditions apply and BMS approval is required.)
- b) Participants who are compulsorily detained for treatment of either a psychiatric or physical (eg, infectious disease) illness are excluded from the study.

Eligibility criteria for this study have been carefully considered to ensure the safety of the study participants and that the results of the study can be used. It is imperative that participants fully meet all eligibility criteria.

6.3 Lifestyle Restrictions

Not applicable. No restrictions are required.

6.4 Screen Failures

Screen failures are defined as participants who consent to participate in the clinical study but are not subsequently entered in the study. A minimal set of screen failure information is required to ensure transparent reporting of screen failure participants, to meet the Consolidated Standards of Reporting Trials (CONSORT) publishing requirements, and to respond to queries from regulatory authorities. Minimal information includes date of consent, demography, screen failure details, eligibility criteria, and any serious AEs.

6.4.1 Retesting During Screening or Lead-In Period

Participant Re-enrollment: This study permits the re-enrollment of a participant that has discontinued the study as a pre-treatment failure (ie, participant has not been treated). If re-enrolled, the participant must be re-consented. Retesting of laboratory parameters and/or other assessments within any single screening period will be permitted (in addition to any parameters that require a confirmatory value). The most current result prior to treatment is the value by which study inclusion will be assessed, as it represents the participant's most current, clinical state.

Laboratory parameters and/or assessments that are included in [Table 2-1](#) may be repeated in an effort to find all possible well-qualified participants. Consultation with the medical monitor may be needed to identify whether repeat testing of any particular parameter is clinically relevant.

7 TREATMENT

Study treatment is defined as any investigational treatment(s), marketed product(s), placebo, or medical device intended to be administered to a study participant according to the treatment allocation.

Study treatment includes Investigational [Medicinal] Product (IP/IMP) and can consist of the following:

- BMS-986205
- Nivolumab

Product description and storage information are described in [Table 7-1](#). Preparation, administration, and storage instructions will be provided separately. An IP, also known as IMP in some regions, is defined a pharmaceutical form of an active substance or placebo being tested or used as a reference in a clinical study, including products already with a marketing authorization but used or assembled (formulated or packaged) differently than the authorized form, or used for an unauthorized indication, or when used to gain further information about the authorized form.

Other medications used as support or escape medication for preventative, diagnostic, or therapeutic reasons, as components of the standard of care for a given diagnosis, may be considered as non IP. Not applicable for this study.

Table 7-1: Study Treatments for CA017076

Product Description / Class and Dosage Form	Potency	IP/Non-IMP	Blinded or Open Label	Packaging / Appearance	Storage Conditions (per label)
BMS-986205	100 mg	IP	Open Label	Tablet	Refer to the label on container and/or pharmacy manual
BMS-986205	50 mg	IP	Open Label	Tablet	Refer to the label on container and/or pharmacy manual
Nivolumab Solution for Injection	10 mg/mL (100-mg/vial)	IP	Open Label	Vial	Refer to the label on container and/or pharmacy manual

7.1 Treatments Administered

The selection and timing of dose for each participant is shown in Table 7.1-1:

Table 7.1-1: Selection and Timing of Dose

Study Treatment	Unit dose strength(s)/Dosage level(s)	Dosage formulation Frequency of Administration	Route of Administration
BMS-986205	100 mg/tablet	1 tablet/daily	Oral
Nivolumab	480 mg	Solution for injection/ every 4 weeks	IV

7.1.1 BMS-986205 Administration

A bottle of BMS-986205 should be dispensed to participants at Day 1 of each cycle.

BMS-986205 is administered as a tablet. The tablet must be administered by mouth, swallowed whole, and not be crushed, chewed, dissolved, or altered in any way. BMS-986205 100 mg oral daily dose must be administered with a meal at approximately the same time each day. On the morning of Cycle 0 Days 1 and 14, and Cycle 1 Day 1 when serial PK samples are collected, after fasting for at least 10 hours, each participant will receive a single oral dose of BMS-986205 within approximately 5 minutes of completing a meal. At the time of dosing, approximately 240 mL of water will be administered to the participant along with BMS-986205. The time of BMS-986205 administration will be called “0” hour.

7.1.2 Nivolumab Administration

During combination therapy, infusion of nivolumab should start approximately 30 minutes following BMS-986205. Nivolumab should be infused over 30 minutes. Further details regarding preparation and administration will be provided separately in site/pharmacy materials. Restrictions related to food and fluid intake are described in [Section 7.7.2](#).

7.2 Method of Treatment Assignment

Enrolled participants, including those not dosed, will be assigned sequential participant numbers starting with 00001 (eg, 00001, 00002, 00003.... 00010). Those enrolled participants meeting inclusion and exclusion criteria will be eligible to be dosed.

7.4 Dosage Modification

The sponsor will carefully review the totality of the safety data observed among the 12 Chinese patients treated with nivolumab and BMS-986205. If such review suggests that the risk profile of the treatment regimen deviates significantly from that observed among non-Chinese patients treated with this same regimen, then consideration will be given to studying a lower dose of

BMS-986205 in combination with nivolumab or enrolling additional Chinese patients to confirm the safety of the protocol defined treatment regimen.

7.4.1 Guidelines For Dose Modification

A dose reduction of BMS-986205 is defined as a change from a 100 mg QD tablet to a 50 mg QD tablet.

Doses of BMS-986205 should be reduced for the following AEs attributable to study therapy that do not otherwise meet criteria for discontinuation:

- Grade 3 fatigue, nausea, vomiting, or anemia related to study treatment
- Methemoglobin $\geq 15\%$
- Clinically significant elevations in methemoglobin (generally 10%, with a normal hemoglobin level⁴²) with any associated Grade 3 AE (hypoxia, dyspnea, confusion, etc.) attributable to sustained elevations of methemoglobin and not attributable to another etiology
- QTcF > 500 msec confirmed by at least 1 repeat ECG and at least 60 msec above baseline (see [Appendix 9](#))

Dose modification and interruption of BMS-986205 may occur in the setting of lower grade AEs and/or be more conservative than indicated above based on the clinical judgment of the investigator after consultation with the BMS Medical Monitor and should be well documented. For an AE requiring dose modification, BMS-986205 should be interrupted to allow improvement of the AE, even if the AE does not otherwise meet criteria for dose delay (Section 7.4.2).

Re-escalation of BMS-986205 will not be permitted once the dose of BMS-986205 has been reduced for a participant.

Only one dose reduction is permitted. The participant must discontinue study treatments if a subsequent dose reduction of BMS-986205 is required (see [Section 7.4.4](#)).

There will be no dose escalations or reductions of nivolumab allowed. For Q4W dosing cycles, participants may be dosed within a ± 3 day window. For this dosing cycle, participants may be dosed no less than 25 days and no more than 31 days between doses. In extenuating circumstances in which the participant cannot make the dosing schedule within the 3-day window, the BMS medical monitor/designee should be contacted.

Premedications are not recommended for the first dose of nivolumab.

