7.4.2 Dose Delay due to Toxicity

BMS-986205 and nivolumab administration should be delayed for the following:

- Grade 2 non-skin, drug-related AE, with the exception of fatigue, nausea, vomiting, and anemia
- Grade 2 drug-related creatinine, AST, ALT, and/or total bilirubin abnormalities
- Grade 3 drug-related skin AE
- Grade 3 drug-related fatigue, nausea, vomiting, diarrhea, and anemia
- Grade 3 drug-related laboratory abnormality, with the following exceptions:

- Grade 3 lymphopenia or asymptomatic amylase or lipase elevations do not require dose delay
- Grade ≥ 3 AST, ALT, total bilirubin will require dose discontinuation (see [Section 7.4.4](#))
- Any AE, laboratory abnormality, or intercurrent illness that, in the judgment of the investigator, warrants delaying the dose of study medication (should consult the BMS medical monitor and should be well documented)

In addition, **only BMS-986205** should be delayed for the following:

- Methemoglobin $\geq 15\%$
- Clinically significant elevations in methemoglobin (generally 10% with a normal hemoglobin level⁴²) with any associated Grade 3 AE (hypoxia, dyspnea, confusion, etc.) attributable to sustained elevations of methemoglobin and not attributable to another etiology
- QTcF > 500 msec confirmed by at least 1 repeat ECG and at least 60 msec above baseline (see [Appendix 9](#)).

Participants may continue to receive nivolumab during dose delays of BMS-986205 for elevations of methemoglobin and associated events, as well as QTcF prolongations.

For participants with methemoglobin elevations with associated Grade 3 AEs, if contribution of nivolumab to the associated AE cannot be ruled out (eg, a participant with dyspnea in whom pneumonitis has not yet been ruled out), nivolumab dosing should be delayed as well. See [Section 7.4.6](#) for management of methemoglobinemia.

If BMS-986205 dosing is delayed, dose reduction may be necessary, see [Section 7.4.1](#).

If dosing is resumed after a delay, BMS-986205 may be resumed as soon as the criteria to resume treatment are met (see [Section 7.4.3](#)). Nivolumab should be resumed as soon as possible after criteria to resume treatment are met but may be resumed later than BMS-986205 given the differences in each drug's administration.

Participants who require delay of any study treatment should be re-evaluated weekly or more frequently if clinically indicated and resume dosing when re-treatment criteria are met.

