7.4.3 Criteria to Resume Treatment of BMS-986205 and Nivolumab

Participants may resume treatment with study treatments when the drug-related AE(s) resolve to Grade ≤ 1 or baseline value, with the following exceptions:

- Participants may resume treatment in the presence of Grade 2 fatigue.
- Participants who have not experienced a Grade 3 drug-related skin AE may resume treatment in the presence of Grade 2 skin toxicity.
- For participants with Grade 2 AST, ALT, and/or total bilirubin abnormalities, dosing may resume when laboratory values return to baseline and management with corticosteroids, if needed, is complete.

- Participants with combined AST/ALT AND total bilirubin values meeting discontinuation parameters (Section 7.4.4) should have treatment permanently discontinued.
- Drug-related pulmonary toxicity, diarrhea, or colitis must have resolved to baseline before treatment is resumed. Participants with persistent Grade 1 pneumonitis after completion of a steroid taper over at least 1 month may be eligible for retreatment if discussed with and approved by BMS medical monitor/designee.

Participants with drug-related endocrinopathies adequately controlled with only physiologic hormone replacement may resume treatment after consultation with the BMS medical monitor/designee. Adrenal insufficiency requires discontinuation regardless of control with hormone replacement.

For participants who have BMS-986205 held for elevations of methemoglobin, dosing may resume when the methemoglobin levels have decreased to below the institutional ULN and any associated AEs have resolved to Grade \leq 1 or baseline value. Dose modification of BMS-986205 should be considered when resuming after a delay (see [Section 7.4.1](#)).

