- Grade 4 drug-related endocrinopathy AEs, such as, hyper- or hypothyroidism, or glucose intolerance, which resolve or are adequately controlled with physiologic hormone replacement (corticosteroids, thyroid hormones) or glucose-controlling agents, respectively, may not require discontinuation after discussion with and approval from the BMS medical monitor/designee.
- Any AE, laboratory abnormality, or intercurrent illness which, in the judgment of the investigator, presents a substantial clinical risk to the participant with continued BMS-986205 and nivolumab dosing
- Any event that leads to delay in dose administration $>$ 10 weeks from the previous dose requires discontinuation, with the following exceptions:
 - Dose administration delays to allow for prolonged steroid tapers to manage drug-related AEs are allowed.
 - Dose administration delays lasting $>$ 10 weeks from the previous dose that occur for non-drug-related reasons may be allowed if approved by the BMS medical monitor/designee.

Prior to re-initiating treatment in a participant with a dose delay lasting $>$ 10 weeks, the BMS medical monitor/designee must be consulted. Tumor assessments should continue as per protocol even if dosing is delayed. Periodic study visits to assess safety and laboratory studies should also continue Q4W or more frequently if clinically indicated during such dosing delays.

- For participants who delay BMS-986205 but continue nivolumab, any dose delay of BMS-986205 lasting $>$ 10 weeks will result in the discontinuation of BMS-986205, but not nivolumab treatment.

All participants who discontinue IP should comply with protocol-specified follow-up procedures as outlined in [Section 2](#). The only exception to this requirement is when a participant withdraws consent for all study procedures including post-treatment study follow-up or loses the ability to consent freely (eg, is imprisoned or involuntarily incarcerated for the treatment of either a psychiatric or physical illness).

If study drug is discontinued prior to the participant's completion of the study, the reason for the discontinuation must be documented in the participant's medical records and entered on the appropriate case report form (CRF) page.

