### 7.4.2 Modifications of Study Therapy

#### 7.4.2.1 Dose Delays

Each BMS-986205 and nivolumab may be delayed.

A dose of nivolumab will be considered as actually delayed if the delay is exceeding 3 days (i.e. greater than or equal to 4 days from scheduled dosing date) for nivolumab/IDO1 inhibitor.

BMS-986205 is administered as a tablet daily. A dose of BMS-986205 will be considered as actually delayed (interrupted) if BMS-986205 was not administrated for at least 1 day. Interruption means the continuous oral dosing was stopped or held for a period of time prior to resuming.

All study drugs must be delayed until treatment can resume. Reason for dose delay will be retrieved from CRF dosing pages.

The following parameters will be summarized by study drug:

- Number of subjects with at least one dose delayed, the number of dose delays per subject, the reason for dose delay and the length of dose delay.

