#### **7.4.2.4 *Dose Reductions***

Dose reductions (within subject) are not permitted for nivolumab/IDO1 inhibitor.

Number of subjects with at least one dose reduction, the reason for dose reduction, and the number of dose reductions per subject will be summarized for BMS-986205 only.

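### Protocol 7.4.1 ends both drugs at a second required BMS-986205 reduction and cites 7.4.4, which has no such criterion and stops only BMS-986205 for comparable events

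*Protocol*

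**What the plan says.** **Second reduction.** Protocol 7.4.1 defines a reduction as a step from 100 mg to 50 mg daily, permits one, and bars re-escalation. It then says "The participant must discontinue study treatments if a subsequent dose reduction of BMS-986205 is required" and refers to 7.4.4. Section 7 lists two study treatments, BMS-986205 and nivolumab. The current 7.4.4 does not mention a second reduction.

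**Rules that separate the two drugs.** Protocol 7.4.2 delays BMS-986205 alone for methemoglobin of 15% or more, for clinically significant methemoglobin elevation with a Grade 3 event, and for confirmed QTcF above 500 msec. On nivolumab it says: "Participants may continue to receive nivolumab during dose delays of BMS-986205 for elevations of methemoglobin and associated events", and it extends this to QTcF prolongation. Section 7.4.4 limits the stop for serotonin syndrome to BMS-986205. It also says that a BMS-986205 delay of more than 10 weeks, in a participant still receiving nivolumab, "will result in the discontinuation of BMS-986205, but not nivolumab treatment".

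**Dose after a first event.** Protocol 7.4.1: "Doses of BMS-986205 should be reduced for the following AEs attributable to study therapy", with methemoglobin of 15% or more on the list. The methemoglobin paragraph of 7.4.3: "Dose modification of BMS-986205 should be considered when resuming after a delay", referring back to 7.4.1.

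**SAP.** Section 7.4.2.1: "All study drugs must be delayed until treatment can resume". Section 7.4.2.4: "Dose reductions (within subject) are not permitted for nivolumab/IDO1 inhibitor".

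**The concern.** A mandatory stop of both drugs rests on a reference that leads to no matching rule, and the nearest rules treat the two drugs differently. An investigator facing a second methemoglobin elevation can follow 7.4.1 and stop nivolumab. Or the investigator can follow the pointer to 7.4.4, find nothing that applies, and continue nivolumab as 7.4.2 allows.

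At stake is whether a participant keeps nivolumab, and what the per-drug discontinuation, delay and exposure tables then describe. In a study planned around 12 PK-evaluable participants, a single case is visible in those tables. Methemoglobin is measured throughout treatment and has its own management sections, so the situation is foreseeable.

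**Working it through.** The plan gives no figure to reproduce. The check is a comparison of passages, followed by the size per participant.

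**1. Which events are affected.** The reduction rule covers only events outside the discontinuation criteria: "Doses of BMS-986205 should be reduced for the following AEs attributable to study therapy that do not otherwise meet criteria for discontinuation". A second event that reaches this rule has therefore not met 7.4.4, and the stop of both drugs can come only from 7.4.1. Taking the 7.4.1 triggers in turn:

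- Grade 3 fatigue, nausea or vomiting: 7.4.4 already stops both drugs for a recurrent Grade 3 non-skin drug-related event. No conflict in outcome.
- Grade 3 anemia: 7.4.2 delays both drugs, so the protocol does not treat it as specific to BMS-986205.
- Methemoglobin elevation with a Grade 3 event: recurrence of that event can also stop both drugs under 7.4.4.
- Methemoglobin of 15% or more without symptoms: 7.4.4 exempts Grade 3 laboratory abnormalities except thrombocytopenia and liver tests. The conflict is clean here.
- QTcF above 500 msec: delayed for BMS-986205 alone in 7.4.2. The conflict applies unless the event is recorded as a recurrent Grade 3 drug-related AE.

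Section 5.1 bars a participant with drug-related methemoglobin of 15% or more in Cycle 0 from Cycle 1, so the methemoglobin case arises only during combination therapy.

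**2. One participant traced through the text (asymptomatic methemoglobin of 15% or more).**

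| Situation | Passage | BMS-986205 | Nivolumab |
|---|---|---|---|
| First event | 7.4.2 | delayed | may continue |
| Resuming | 7.4.1 | reduction directed | – |
| Resuming | 7.4.3 | modification to be considered | – |
| Recurrence on 50 mg | 7.4.1 | stops | stops |
| Recurrence on 50 mg | 7.4.2 | delayed | may continue (not limited to a first event) |
| Hold of more than 10 weeks | 7.4.4 | stops | does not stop |

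A short recurrence thus has a wider consequence for nivolumab than a hold of more than 10 weeks, and no reason is given.

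**3. Size for nivolumab.** Nivolumab is given on Day 1 of each of up to 12 cycles. If the recurrence falls in Cycle k after that cycle's infusion, the initial doses at stake are 12 − k: 8 for k = 4, 6 for k = 6, 3 for k = 9.

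SAP Table 7.4.1-1 shows which summaries respond. With dosing every 28 days:

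- Stop after 4 doses: cumulative dose 4 × 480 = 1,920 mg; duration (84 + 28)/7 = 16 weeks; intensity 1,920/16 = 120 mg/week; relative intensity 120/(480/4) = 100%.
- All 12 doses: cumulative dose 12 × 480 = 5,760 mg; duration (308 + 28)/7 = 48 weeks; intensity 5,760/48 = 120 mg/week; relative intensity 100%.

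Doses, cumulative dose and duration differ three-fold. Relative dose intensity does not change.

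**4. Size for BMS-986205 after a first event.** Over a stretch of uninterrupted dosing, 50 mg daily is 350 mg/week, or 350/(100 × 7) = 50% relative intensity. At 100 mg it is 100%.

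**5. SAP.** The 7.4.2.1 sentence on delaying all drugs contradicts the BMS-986205-only delay in protocol 7.4.2. The same SAP section also says that each drug may be delayed and summarises delays by study drug.

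**The case against.** The strongest reply is that 7.4.1 is explicit and 7.4.4 is merely silent. The nivolumab sentence in 7.4.2 governs delays, and the 10-week rule governs a different situation, so the passages can coexist. This stands in part: 7.4.4 does not deny the 7.4.1 rule. It does not explain why 7.4.1 sends the reader to a section with no matching criterion, nor why the neighbouring rules for the same events keep nivolumab.

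On dose at resumption, 7.4.3 refers to 7.4.1 and covers every methemoglobin hold, including holds below the 7.4.1 triggers. That difference is therefore one of strength. The remark in 7.4.2 that a reduction may be needed after a delay covers all causes and defers to 7.4.1; it is not a further conflict.

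Some stronger readings are tempting but not supported:

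- That the 7.4.1 stop is not binding because 7.4.4 omits it. Section 8.1 lists many other mandatory reasons, including investigator judgement and protocol-defined reasons.
- That sites would diverge. Appendix 2 calls this a single-site protocol, although the SAP plans enrollment by country and site.
- That the incidence of AEs leading to discontinuation, a primary endpoint, must change. SAP 7.1.1 counts a subject once when a study drug is withdrawn, so if BMS-986205 stops, the subject counts whether or not nivolumab also stops.
- That an event in Cycle 3 costs nine nivolumab cycles. Nivolumab is at risk only at a recurrence, after recovery and resumption.
- That SAP 7.4.2.4 forbids BMS-986205 reductions. Its next sentence summarises them for BMS-986205 only, and the same combined label is used loosely for nivolumab in SAP 7.4.2.1 and 7.7.

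**Conclusion.** The point holds for asymptomatic methemoglobin of 15% or more and for QTcF prolongation. At a second required reduction, 7.4.1 stops both drugs by reference to a criterion that 7.4.4 does not contain, while 7.4.2 and 7.4.4 otherwise confine BMS-986205-specific holds and stops to that drug. The gap between 7.4.1 and 7.4.3 is a lesser inconsistency. The SAP 7.4.2.1 sentence contradicts the protocol, though its by-drug tabulation plan is unaffected.

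The size is up to 12 − k initial nivolumab doses per affected participant, and 50 versus 100 mg of BMS-986205 daily after a first event. One participant is 1/12 = 8.3 percentage points of 12. The treated denominator may be larger, because Section 5.2 replaces participants who leave at or before Cycle 1 Day 1. The documents give no event rate, so no expected number of cases can be stated.

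This assumes that the methemoglobin finding is a laboratory abnormality below Grade 4 with no recurrent Grade 3 event, and that the QTcF event is not recorded as a recurrent Grade 3 AE. Otherwise 7.4.4 stops both drugs as well. The summary of changes records that a criterion on more than one reduction was removed from 7.4.4. That is background only; the point rests on the current text and implies no view on which rule was intended.

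**What to change.** 1. Reconcile protocol 7.4.1 with 7.4.4, so that one passage states what happens at a second required BMS-986205 reduction and to which drug or drugs it applies. The cross-reference should lead to that passage.
2. Reconcile 7.4.1 with 7.4.3 on whether reduction is required or optional for each listed trigger.
3. Correct the SAP 7.4.2.1 sentence so that it reflects the single-drug delays in protocol 7.4.2.
4. Replace the combined label in SAP 7.4.2.4 with the name of the drug meant.

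Which clinical rule stands in items 1 and 2 is for the sponsor's clinical team. The cost is a protocol clarification and two SAP sentences, with no added participants, visits or procedures.
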